## **2.6 Treatments (study drug, concomitant therapies, compliance)**

The Safety Set will be used for all medication data summaries and listings unless otherwise specified. Summaries will be produced by study arm and for all patients. Listing will be produced by study arm.

### **Study drug and study treatment**

Study drug and study treatment both refer to LDK378 (ceritinib) and will be used interchangeably.

### **Date of first/last administration of study drug**

The date of first administration of study drug is defined as the first date when a non-zero dose of study drug was administered and recorded on the Dosage Administration Record (DAR) eCRF. For the sake of simplicity, the date of first administration of study drug will also be referred to as start date of study drug.

The date of last administration of study drug is defined as the last date when a non-zero dose of study drug was administered and recorded on the DAR eCRF. This date will also be referred to as the last date of study drug.

### **Study day**

CONFIDENTIAL - For Business Use Only

The study day for all assessments (e.g. tumor assessment, death, disease progression, tumor response, performance status, adverse event onset, laboratory abnormality occurrence, vital sign measurement, dose interruption etc.) will be calculated using the start date of study drug as the origin. For assessments occurring after or on the start date of study drug, study day will be calculated as:

$$\text{Study Day} = \text{Date of the assessment/ Event date} - \text{start date of study drug} + 1.$$

The first day of study drug is therefore study day 1.

For any assessment or events such as baseline disease characteristics or medical history (e.g., time since diagnosis of disease) occurring prior to the start of the study drug, study day will be negative and will be calculated as:

$$\text{Study Day} = \text{Event date} - \text{start date of study drug}.$$

The study day will be displayed in the relevant data listings.

## Baseline

Baseline is the result of an investigation describing the “true” uninfluenced state of the patient.

For efficacy evaluations, the last non-missing assessment, including unscheduled assessments on or before the date of start of study treatment is taken as “baseline” value or “baseline” assessment.

For safety evaluations, the last available assessment on or before the date of start of study treatment is taken or “baseline” assessment.

If an assessment is planned to be performed prior to the first dose of study treatment in the protocol and the assessment is performed on the same day as the first administration of study treatment, it will be assumed that it was performed prior to study treatment administration, if assessment time point is not collected or is missing.

If assessment time points are collected, the observed time point will be used to determine pre-dose on study day 1 for baseline calculation. Unscheduled assessments will be used in the determination of baseline. See [Section 4.7.2](#) for further details on derivation of baseline for laboratory data and ECGs.

Patients who start treatment and discontinue from the study on the same day may have two different sets of data collected on study day 1, one being reported to the cycle 1 day 1 visit, the other reported to the end of treatment (EOT) visit. Data reported at the EOT visit are not eligible for baseline selection.

## Dose exposure and intensity

Definitions of duration of exposure, cumulative dose, average daily dose, dose intensity (DI), relative dose intensity (RDI), as well as intermediate calculations, include:

- Duration of exposure (days): last date of study drug – first date of study drug + 1 (periods of interruption are not excluded)
- Cumulative dose (mg): total dose of study drug taken by a patient in the study
- Number of dosing days (days): duration of exposure – number of zero dose days

- Average daily dose (mg/day): cumulative dose (mg)/ number of dosing days (days)
- DI (mg/day): cumulative dose (mg)/ duration of exposure (days)
- RDI (%):  $100 \times [\text{DI (mg/day)}/\text{planned dose intensity (750 mg/day)}]$

Note: given the planned ceritinib dose of 750 mg/day, the planned dose intensity can be calculated as:

$$\text{PDI (mg/day)} = \text{cumulative planned dose (mg)}/\text{Duration of exposure (days)},$$

where

$$\text{cumulative planned dose (mg)} = \text{Protocol planned dose of 750 (mg)} * \text{Duration of exposure.}$$

then, RDI (%) which is calculated as  $100 * \text{DI}/\text{PDI}$  can be simplified as shown above.

Duration of exposure to study drug, cumulative dose, average daily dose, DI and RDI will be summarized by study arm and for all patients. In addition, the duration of exposure to study drug will be categorized into time intervals and frequency counts and percentages of patients with exposure in each time interval will be presented. Frequency counts and percentages of patients who have dose changes, reductions or interruptions, and the corresponding reasons, will be summarized by study arm and for all patients. Time to first dose reduction and time to first dose interruption will be summarized by study arm and for all patients, using summary statistics along with frequency counts and percentages for pre-specified time intervals

Listings of all doses of the study drug along with dose change and dose interruption reasons will be produced.

[Section 4.5](#) provides further details on the definition of dose changes and interruptions.

### Concomitant therapy

Concomitant therapies are defined as any medications (excluding study drug, prior antineoplastic treatments and blood transfusions), surgeries or procedures (including physical therapy) administered in the study and are recorded in the Prior and Concomitant Medications and the Surgical and Medical Procedures eCRF, respectively.

Concomitant medications will be coded using the WHO Drug Reference Listing (WHO DRL) dictionary that employs the WHO Anatomical Therapeutic Chemical (WHO ATC) classification system. Surgeries or procedures will be coded using the Medical Dictionary for Regulatory Activities (MedDRA) terminology. All summaries will be tabulated using frequency counts and percentages by study arm.

Concomitant therapies will be summarized by ATC class and preferred term by study arm and for all patients. These summaries will include: 1) medications starting on or after the start of study drug but starting no later than 30 days after last dose of study drug; and 2) medications starting prior to the start of study drug but continuing after the start of study drug.

All concomitant therapies and surgeries and medical procedures will be listed. Any concomitant therapies starting and ending prior to the start of study drug or starting more than 30 days after the last date of study drug will be flagged in the listings.

CONFIDENTIAL - For Business Use Only

## **Antineoplastic therapy after discontinuation of study drug**

The FAS will be used for all listings and summaries of antineoplastic therapies initiated after discontinuation of study drug. All summaries will be tabulated by study arm and for all patients, using frequency counts and percentages.

Antineoplastic medications initiated after discontinuation of study drug will be summarized by Anatomical Therapeutic Chemical (ATC) class, preferred term and listed.

Antineoplastic radiotherapy since discontinuation of study treatment will be summarized and listed.

Antineoplastic surgery since discontinuation of study treatment will be summarized by primary system organ class and preferred term and listed.

## **2.7 Analysis of the primary variable**

The primary objective is to evaluate the anti-tumor activity of ceritinib in patients with ALK-positive NSCLC metastatic to the brain and/or to leptomeninges.

### **2.7.1 Variable**

The primary endpoint used to evaluate the anti-tumor activity of ceritinib is the overall response rate (ORR), which is defined as the proportion of patients with a best overall confirmed response (BOR) of CR or PR in the whole body, as assessed per RECIST 1.1 by the investigator.

### **Best overall response**

The BOR will be assessed based on reported lesion responses at different evaluation time points. Both CR and PR must be confirmed by repeat assessments performed not less than 4 weeks after the criteria for response are first met. The next scheduled assessment may be used for purposes of confirmation of response.

BOR for each patient is determined from the sequence of overall (lesion) responses according to the following rules:

- CR = at least two determinations of CR at least 4 weeks apart before progression  
PR = at least two determinations of PR or better at least 4 weeks apart before progression (and not qualifying as a CR)
- SD = at least one SD assessment (or better) > 7 weeks after start of study drug (and not qualifying as a CR or PR)
- PD = progression  $\leq$  17 weeks after start of study drug (and not qualifying as a CR, PR or SD)
- UNK = all other cases (i.e. not qualifying for confirmed CR or PR and without SD after more than 7 weeks or progression within the first 17 weeks)

The cut-off for SD too early and PD too late were chosen based on tumor assessment schedule. Only tumor assessments performed before the start of any further anti-neoplastic therapies (i.e. any additional secondary anti-neoplastic therapy or anti-cancer surgery) will be considered in

the assessment of BOR. If a patient receives any further anti-neoplastic therapy while on study, any subsequent assessments will be excluded from the BOR determination. Further anti-neoplastic therapies will be identified from the data collected on ‘Anti-neoplastic therapies since last date of study drug’ as appropriate. Clinical deterioration will not be considered as documented disease progression. Patients with BOR ‘unknown’ will be summarized by reason for having unknown status. The following reasons will be used:

- No valid post-baseline assessment
- All post-baseline assessments have overall response UNK
- New anti-neoplastic therapy started before first post-baseline assessment
- Stable disease (SD) too early ( $\leq 7$  weeks after start date of study drug)
- PD too late ( $> 17$  weeks after start date of study drug).

Special (and rare) cases where BOR is ‘unknown’ due to both early SD and late PD will be classified as ‘SD too early’. In case, a patient had only a non-measurable disease at baseline, same cut-off ( $\leq 7$  weeks after start date of study drug) will be applied for a response of non - CR/non-PD too early.

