4.1.2.1 Tumor assessments during study conduct

Complete tumor assessments including gadolinium enhanced brain MRI will be repeated at Week 8 (on Cycle 3 Day 1) and every 8 weeks (i.e. every 2 cycles) thereafter or earlier if clinically indicated.

Tumor response will be evaluated starting from the first day of treatment with ceritinib until the time of disease progression according to RECIST 1.1 as determined by investigator, withdrawal of consent for further follow-up, loss to follow-up or death. This schedule of

tumor assessment must continue regardless of dose interruptions. In patients who discontinue treatment in the absence of RECIST-defined progression, tumor assessments will continue every 8 weeks until progression of disease, withdrawal of consent for further follow-up, loss to follow-up or death.

For patients presenting with baseline leptomeningeal carcinomatosis with documented malignant cells in the cerebrospinal fluid, CSF samples will be collected at a frequency determined by local clinical practice unless medically contra-indicated. Samples should be obtained from site of disease or initially positive cytology if possible. The investigator may determine if more frequent evaluations are needed in case of suspected disease progression and/or in accordance with local clinical practice. If there are any signs or radiologic or clinical neurological progression, a CSF will be collected if feasible. Clinical progression may be determined based on results of cytological or neurological evaluations.

Gadolinium-enhanced brain MRI scans and all other imaging data collected at baseline and during the conduct of the study will be submitted to the designated imaging vendor for BIRC review.

In this study, standard RECIST 1.1 will be used to evaluate the whole body (including intracranial and extracranial cancer lesions) response endpoints. Assessment of the overall response to treatment and other whole body response related endpoints will be conducted by investigators and BIRC.

Additionally, the intracranial and the extracranial metastatic disease will be evaluated as two separate entities. RECIST 1.1 and RANO for High Grade Glioma ([Wen et al 2010](#)) criteria will be used to determine intracranial tumor response based on target brain lesions, if applicable, any non-target brain lesions and any new brain lesions. RECIST 1.1 will be used to evaluate the extracranial tumor response but brain will be excluded from the evaluation.

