7.1 Study flow and visit schedule

Table 7-1 lists all of the assessments and indicates with an “X” the visits when they are performed. Each treatment cycle is 28 days (the 28 days cycle length is fixed regardless of whether the dose of ceritinib is withheld). All visits are to be scheduled according to the appropriate number of calendar days from Cycle 1 Day 1 of study drug administration. A visit window of +/- 1 day in Cycle 1 and +/- 3 days in Cycle 2 onwards is allowed. Imaging evaluations may be performed +/-7 days of the due date of the assessment. **Note: If treatment with ceritinib is withheld at any time during the study, all study visits, safety and efficacy assessments should continue according to the appropriate number of calendar days from Cycle 1 Day 1 as per the schedule of assessments.**

[figure not shown]
All data obtained from these assessments must be supported in the patients’ source documentation. No eCRF will be used as a source document. The table indicates which assessments produce data to be entered into the database (D) or remain in the source documents only (S).

Table 7-1 Visit evaluation schedule

Visit name	Category	Protocol section	Molecular Pre-Screening	Screening Phase (Day -28 to Day -1)		Treatment Phase					Post treatment follow up phase		Survival follow-up phase
				General Screening	Brain specific evaluation (Day -14 to Day -1)	Cycle 1 (28 days)			Subsequent cycles (28 days)	End of treatment (EOT)	Tumor follow-up if no PD - at the EOT	End of post-treatment evaluation (Study Phase completion)	
						Cycle 1 Day 1	Cycle 1 Day 8	Cycle 1 Day 15	Cycle 2 Day 1; Cycle 3 Day 1; etc.	End of treatment visit			
Obtain molecular pre-screening ICF and IRT registration	D	7.1.2.	X										
Collect tumor biopsy, either archival or new tumor sample for ALK rearrangement testing	D	7.1.1.	X										
ALK test performed on archival specimen or in newly obtained tumor tissue biopsy at NVS central laboratory	D	7.1.1.1.	X										
Confirmation of ALK status by central laboratory	D	7.1.1. 7.1.2.	X										
Obtain Main Informed Consent and IRT registration	D	7.1.2.	X* (see footnote)	X									

	Category	Protocol section		Screening Phase (Day -28 to Day -1)		Treatment Phase					Post treatment follow up phase		Survival follow-up phase

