7.1.3 Treatment period

The study treatment phase begins on Cycle 1, Day 1 with the first administration of ceritinib. Treatment with ceritinib will continue until the patient experiences disease progression (in the brain, outside of the brain or both) as determined by the investigator according to RECIST 1.1, unacceptable toxicity that precludes further treatment, pregnancy, start of a new anticancer therapy, discontinues treatment at the discretion of the patient or investigator, lost to follow-up, death, or study is terminated by Sponsor. Exceptions to the discontinuation of study drug upon confirmation of PD by the investigator are detailed in [Section 4.1.2.2](#).

Patients will be assessed as per visit schedule in [Table 7-1](#).

Visit windows of ± 1 calendar day will be applicable to scheduled study assessments during Cycle 1. Visit windows of ± 3 days from scheduled study assessments will apply during and beyond Cycle 2. The only exception is imaging assessments, which have a ± 7 day window at all scheduled time points.

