7.2 Assessment types

7.2.1 Efficacy assessments

Whole body and extracranial tumor response will be assessed by investigator and by BIRC according to the Novartis guideline version 3.1 ([Appendix 2](#)) based on RECIST 1.1 ([Eisenhauer et al 2009](#)).

Additionally, intracranial tumor response will be assessed by investigator and by BIRC using modified RECIST 1.1 and the Response Assessment in Neuro-Oncology (RANO) criteria for high grade gliomas ([Wen et al 2010](#)) ([Appendix 3](#)).

Imaging data will be centrally collected and checked for quality by an imaging Contract Research Organization (CRO) designated by Novartis. Patient neurological status, corticosteroid dose and cytology results, as well as, information regarding prior interventions and pre-existing radiographic findings that mimic metastatic disease at baseline/screening, should also be transmitted to the imaging CRO for review by BIRC. Further details regarding transmission of the information can be found in the imaging CRO site operations manual.

The imaging assessment collection plan is presented in [Table 7-2](#).

Table 7-2 Imaging assessment collection plan

Procedure	Screening/Baseline	During Treatment/Follow-up
CT or MRI of Chest and Abdomen	Mandated	Mandated at week 8 on Cycle 3 Day 1, then every 2 nd cycle (i.e., every 8 weeks)
Gadolinium enhanced MRI of the brain	Mandated	Mandated at week 8 on Cycle 3 Day 1, then every 2 nd cycle (i.e., every 8 weeks)
Whole body bone scan	Mandated	If clinically indicated

 • Spine MRI (for suspected LC patients only) • CT scan or MRI of other metastatic sites (e.g., neck, pelvis, etc.) • Localized bone CT scan, MRI or x-ray (for any lesions identified on the whole body bone scan that are not visible on the chest/abdomen (and pelvis if applicable) CT scan or MRI) • Photography (for any skin lesions) 	Only if clinically indicated	At week 8 on Cycle 3 Day 1, then every 2 nd cycle (i.e., every 8 weeks) only if positive at baseline or clinically indicated

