- PR = at least two determinations of PR or better at least 4 weeks apart before progression (and not qualifying for a CR) where confirmation required or one determination of PR prior to progression where confirmation not required
- SD = at least one SD assessment (or better) > 6 weeks after randomization/start of treatment (and not qualifying for CR or PR).
- PD = progression ≤ 12 weeks after randomization/ start of treatment (and not qualifying for CR, PR or SD).
- UNK = all other cases (i.e. not qualifying for confirmed CR or PR and without SD after more than 6 weeks or early progression within the first 12 weeks)

Overall lesion responses of CR must stay the same until progression sets in, with the exception of a UNK status. A patient who had a CR cannot subsequently have a lower status

other than a PD, e.g. PR or SD, as this would imply a progression based on one or more lesions reappearing, in which case the status would become a PD.

Once an overall lesion response of PR is observed (which may have to be a confirmed PR depending on the study) this assignment must stay the same or improve over time until progression sets in, with the exception of an UNK status. However, in studies where confirmation of response is required, if a patient has a single PR ($\geq 30\%$ reduction of tumor burden compared to baseline) at one assessment, followed by a $< 30\%$ reduction from baseline at the next assessment (but not $\geq 20\%$ increase from previous smallest sum), the objective status at that assessment should be SD. Once a confirmed PR was seen, the overall lesion response should be considered PR (or UNK) until progression is documented or the lesions totally disappear in which case a CR assignment is applicable. In studies where confirmation of response is not required after a single PR the overall lesion response should still be considered PR (or UNK) until progression is documented or the lesion totally disappears in which case a CR assignment is applicable.

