### 2.8.1.1 Key secondary endpoint

The key secondary objective is to evaluate Disease Control Rate (DCR). The DCR is defined as the proportion of patients with best overall response (BOR) of CR, PR or SD in the whole body, as assessed per RECIST 1.1 by the investigator.

DCR will be estimated and the exact binomial 95% CI (Clopper & Pearson, 1934) will be presented by study arm and for all patients.

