### 3 Changes to protocol specified analyses

Table 3-1 summarizes the changes to protocol-specified analyses and associated rationale for inclusion in Appendix 16.1.9 (Documentation of Statistical Methods) of the CSR.

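### Read as elapsed time, the SAP's > 7-week minimum for stable disease rejects a scan on the first permitted Week 8 day, and Table 3-1 does not list the change from the protocol's > 6 weeks

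*SAP*

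**What the plan says.** The protocol applies its Appendix 2 to whole-body and extracranial response: "Whole body and extracranial tumor response will be assessed by investigator and by BIRC according to the Novartis guideline version 3.1". Section 14.2.17 of that appendix gives the minimum time for stable disease: "SD = at least one SD assessment (or better) > 6 weeks after randomization/start of treatment". It accepts progression as best response up to 12 weeks.

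SAP 2.7.1 uses different values: "SD = at least one SD assessment (or better) > 7 weeks after start of study drug". Progression counts up to 17 weeks. SD at or before 7 weeks becomes unknown with the reason 'SD too early', and the same limit applies to non-CR/non-PD. The SAP says both cut-offs were derived from the imaging schedule.

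The key secondary endpoint depends on this rule: "The DCR is defined as the proportion of patients with best overall response (BOR) of CR, PR or SD in the whole body". SAP 2.8.1.2.1 and 2.8.1.2.2 carry it into IDCR and EDCR at Weeks 8 and 16.

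On timing, protocol 4.1.2.1 says that tumor assessments "will be repeated at Week 8 (on Cycle 3 Day 1) and every 8 weeks". Protocol 7.1 adds "Each treatment cycle is 28 days", and protocol 7.1.3 sets the tolerance: "The only exception is imaging assessments, which have a ± 7 day window at all scheduled time points".

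SAP Section 3 states: "Table 3-1 summarizes the changes to protocol-specified analyses and associated rationale". The table has two rows, one on the summary method for time to response and one on PFS censoring at new anticancer therapy. Neither best-response cut-off appears.

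**The concern.** A cut-off taken from the imaging schedule should accept every scan made within its permitted window. This one appears to exclude the first permitted day, so a patient scanned on schedule and found stable could be counted as not controlled. The SAP also does not say how a week is to be converted to days, so the programmer has to choose, and the choice decides which on-schedule scan is misclassified.

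Separately, the cut-offs differ from the protocol's, and the table meant to list such differences in the CSR appendix is silent on them.

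**Working it through.** **The plan's own figure.** SAP Table 2-5 gives 91/140 = 65% with an exact 95% CI of 56.49% to 72.86%. The Clopper-Pearson limits are the 2.5% quantile of Beta(91, 50) and the 97.5% quantile of Beta(92, 49), which reproduce it. The other seven rows also reproduce, so the precision table is not in question.

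**Schedule in days** (protocol 4.1.2.1, 7.1 and 7.1.3; SAP 2.6 for first dose = Day 1).

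- Week 8 = Cycle 3 Day 1 = 2 × 28 + 1 = Day 57; window 57 ± 7 = Days 50 to 64.
- Week 16 = Cycle 5 Day 1 = 4 × 28 + 1 = Day 113; window 113 ± 7 = Days 106 to 120.
- Weeks after start = (study day − 1)/7.

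**SD edge.**

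| Study day | Days after start | Weeks | Protocol > 6 weeks, elapsed | SAP > 7 weeks, elapsed | SAP > 7 weeks, +1 count |
|---|---|---|---|---|---|
| 44 | 43 | 6.14 | counts | no | no |
| 49 | 48 | 6.86 | counts | no | no |
| 50 | 49 | 7.00 | counts | no | counts (50 > 49) |
| 51 | 50 | 7.14 | counts | counts | counts |

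On the elapsed reading the protocol and SAP differ on Days 44 to 50. Only Day 50 lies inside the permitted Week 8 window.

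**PD edge.** Day 120 is 119 days = 17.0 weeks after start, so it meets ≤ 17 weeks. With the +1 count it is 120 days > 119 and becomes 'PD too late'. Neither count fits both window edges.

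**Which count applies.** The rule is worded as time after the start date, which is elapsed time. The SAP's Week 8 window for IDCR, Days 29 to 85, agrees: (29 − 1)/7 = 4.0 and (85 − 1)/7 = 12.0, that is 8 ± 4 weeks. Against this, protocol 14.2.34 and the follow-up formula in SAP 2.8.1.2.3 compute durations as end − start + 1.

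**Where it acts.** Overall DCR, IDCR and EDCR lose a patient only if Day 50 holds the sole SD-or-better evidence; a later qualifying scan restores the patient. The Week 8 rates are more exposed. An SD on Day 50 that is the latest scan in Days 29 to 85 is set to unknown, and the next scheduled scan (Day 113) lies outside that window. ORR has no minimum-time rule and does not change.

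**Size.** One patient is 1/138 = 0.7 points in Arms 1-4 as enrolled (42 + 40 + 12 + 44 = 138, protocol Amendment 6). Starting from the planned 91/140 and moving k patients from SD to unknown:

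| k | DCR | Exact 95% CI |
|---|---|---|
| 1 | 64.29% | 55.75% to 72.20% |
| 2 | 63.57% | 55.02% to 71.53% |
| 3 | 62.86% | 54.29% to 70.87% |

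The planned lower bound above 55% is lost at k = 3.

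The documents give no scan-timing data, so any expected number rests on assumptions. Take SD in 20.7% (protocol Table 1-2, a different study under RECIST 1.0) and 30% to 50% of those patients with no later SD-or-better scan.

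- Day 50 alone: with first scans uniform over 15 days, the share on Day 50 is at most 1/15 = 6.7%. It is (1/15)² = 0.44% if two independent scans must both fall there. The loss is 0.0044 × 0.207 × 0.3 = 0.03 points to 0.067 × 0.207 × 0.5 = 0.7 points.
- Days 44 to 50 (the difference from the protocol): with 3% to 15% of first scans there, 0.03 × 0.207 × 0.3 = 0.2 points to 0.15 × 0.207 × 0.5 = 1.6 points.

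**The case against.** Much of the defence stands.

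- The protocol permits this route. Section 14.2.29 lets study-specific departures be defined in the analysis plan, and SAP Section 1 says its decisions were made before database lock. The 6- and 12-week values sit in a generic appendix, and the study's own DCR definition (protocol 10.5.1) sets no minimum time. Choosing 7 weeks is allowed.
- The rule is not hidden. The SAP's document history records the update, Section 2 will be imported into the CSR, and unknown responses will be tabulated by reason, including 'SD too early'. A reader might infer that the CSR would pass the DCR off as protocol-defined. The documents do not support that: the CSR will show the rule and the count, and only its list of changes would fail to flag the difference.
- Declining to credit SD on Days 44 to 49, before the first scheduled window opens, is a coherent choice. It can only lower DCR.
- With the +1 count Day 50 passes. The remaining error moves PD to unknown on Day 120, and neither category counts in DCR or ORR.
- A stable assessment is dated by its latest scan (protocol 14.2.25, SAP 4.8.5), so a whole-body assessment falls on Day 50 only if all its imaging is done by then.

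These points limit the consequence. They do not make the cut-off fit the schedule it is said to follow, and they do not settle which day count applies.

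**Conclusion.** The point holds as a small error of specification. On the literal elapsed-time reading, which the SAP's own Week 8 window supports, an on-schedule scan on Day 50 is scored too early. On the other reading the error moves to Day 120 and leaves DCR alone. Table 3-1 omits both changes, SD from > 6 to > 7 weeks and PD from ≤ 12 to ≤ 17 weeks; the PD change moves patients between PD and unknown and does not alter DCR.

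Under the assumptions above, the expected effect on overall DCR is below one point for Day 50 and at most about 1.6 points for the full difference from the protocol. The trial estimates rates and tests no hypothesis.

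Two stronger readings should be resisted. One is that the effect is material in Arms 3 and 5. The figures of 8.3 and 5.6 points are simply 1/12 and 1/18, one patient in a small arm; applying 0.2% to 1.6% to those arms gives about 0.02 to 0.19 and 0.03 to 0.28 expected patients. The other is that an SAP amended in March 2019, after enrolment ended in August 2017, points to a results-driven change. Nothing in the documents shows that.

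**What to change.** In SAP 2.7.1, state the cut-offs in study days:

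- SD (and non-CR/non-PD) counts on study day ≥ 50, that is ≥ 49 days after start; 'SD too early' is study day < 50.
- PD counts on study day ≤ 120, that is ≤ 119 days after start; 'PD too late' is study day > 120.

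Both window edges are then inclusive and no week-to-day conversion is left open. The IDCR and EDCR rules inherit the change by cross-reference.

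Add one row to Table 3-1 with the protocol 14.2.17 values (> 6 weeks, ≤ 12 weeks), the SAP values and the reason. The row is still needed after the correction, because SD on Days 44 to 49 would continue to count under the protocol and not under the SAP. A single DCR line under the > 6-week rule is optional.

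The cost is a few words of SAP text, one table row and a small programming check. No trial procedure changes.
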